#### 3.2 Secondary

- a) SOM1a: Comparison of the proportion of participants reporting at least one solicited reactogenicity event to include fever, chills, myalgia, or arthralgia of moderate or greater severity in the Simultaneous group with the Sequential group within 1-7 days following Vaccination Visit 1 visit during which participants receive either IIV4 or placebo with an mRNA COVID-19 vaccine.
- b) SOM2a: Comparison of the proportion of participants reporting at least one solicited reactogenicity event to include fever, chills, myalgia, or arthralgia of moderate or greater severity in the Simultaneous group with the Sequential group within 1-7 days following Vaccination Visit 2 during which participants receive either IIV4 or placebo without an mRNA COVID-19 vaccine.
- c) SOM3a: The proportion of participants in each vaccination group reporting specified solicited local and systemic reactogenicity events of any severity and by severity grade within 1-7 days following the first vaccination visit during which participants receive either IIV4 or placebo with an mRNA COVID-19 vaccine.

SOM3b: The proportion of participants in each vaccination group reporting specified solicited local and systemic reactogenicity events of any severity and by severity grade within 1-7 days following the second vaccination visit during which participants receive either IIV4 or placebo.

SOM3c: The proportion of participants in each vaccination group reporting specified solicited local and systemic reactogenicity events of any severity and by severity grade within 1-7 days following the third vaccination visit during which all participants receive an mRNA COVID-19 vaccine alone for those receiving two doses of mRNA COVID-19 vaccine.

- d) SOM4a: The proportion of participants in Simultaneous and Sequential Groups with at least one serious adverse event occurring during the study period and a description of each event.

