BNT162b2 is currently authorized under the FDA EUA for persons 5 – 15 years of age and approved for persons 16 years of age and older, while the mRNA-1273 is approved for persons 18 years of age and older. CDC's Advisory Committee on Immunization Practices (ACIP) has recommended use of these vaccines, according to the specifications in the EUAs; CDC has also published interim clinical considerations for use of COVID-19 vaccines^{17,18}. Both vaccines are administered intramuscularly with the Pfizer-BioNTech vaccine (30 µg, 0.3mL each for persons

≥ 12 years of age and 10 µg, 0.2mL each for persons 5-11 years of age) being administered 21 days apart and the Moderna vaccine (100 µg, 0.5mL each) being administered 28 days apart as a primary series in particular, for populations that include moderately or severely immunocompromised, adults over 65 years of age and those who need rapid protection against COVID-19. Doses should not be administered earlier than recommended but if given within a 4-day period prior to the scheduled time may be considered valid. The second dose can be administered between 3 and 8 weeks after the first dose for the Pfizer- BioNTech vaccine and between 4 and 8 weeks after the first dose for the Moderna vaccine. The vaccines are not considered to be interchangeable, however under extenuating circumstances such as when the brand of the first dose of vaccine is unknown, any mRNA COVID-19 vaccine may be administered 28 days following the first dose¹⁷.

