2 STUDY OBJECTIVES AND OUTCOME MEASURES

OBJECTIVE	OUTCOME
Primary	
1. To compare the proportion of participants with moderate or more severe fever, chills, myalgia, or arthralgia in the group receiving IIV4 simultaneously with mRNA COVID-19 vaccine at Vaccination Visit 1 (Simultaneous group) with the group receiving IIV4 alone one to two weeks later at Vaccination Visit 2 (Sequential group) following both Vaccination Visit 1 and 2 Hypothesis: The proportion of participants with moderate or more severe fever, chills, myalgia or arthralgia will be noninferior (not higher) in the Simultaneous group versus the Sequential group.	1a. Comparison of the proportion of participants reporting at least one solicited reactogenicity event to include fever, chills, myalgia, or arthralgia of moderate or greater severity in the Simultaneous group with the Sequential group within 1-7 days following both Vaccination Visit 1 and Vaccination Visit 2
Secondary	
1. To compare the proportion of participants with moderate or more severe fever, chills, myalgia, or arthralgia in the Simultaneous versus the Sequential Group following the first vaccination visit	1a. Comparison of the proportion of participants reporting at least one solicited reactogenicity event to include fever, chills, myalgia, or arthralgia of moderate or greater severity in the Simultaneous group with the Sequential group within 1-7 days following Vaccination Visit 1 visit during which participants receive either IIV4 or placebo with an mRNA COVID-19 vaccine

2. To compare the proportion of participants with moderate or more severe fever, chills, myalgia, or arthralgia in the Simultaneous versus Sequential Group following the second vaccination visit	2a. Comparison of the proportion of participants reporting at least one solicited reactogenicity event to include fever, chills, myalgia, or arthralgia of moderate or greater severity in the Simultaneous group with the Sequential group within 1-7 days following Vaccination Visit 2 during which participants receive either IIV4 or placebo without an mRNA COVID-19 vaccine

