With Day 1 serving as the initial day of vaccination, participants will be followed through Day 7 (total 7 days) for solicited symptoms of reactogenicity as described in Section 5.4. HRQOL data will be collected during this time period for persons aged ≥ 12 years. Solicited reactogenicity events will also be monitored through Day 7 (total 7 days) following Visit 2 (all participants) and Visit 3 (only those participants receiving primary 2-dose COVID-19 vaccine series). Participants will also be followed for 7 days after each vaccination visit for unsolicited adverse events, through Day 120 for serious adverse events (SAEs) and through Day 120 for adverse events of special interest (AESI), as described in Section 5.4.

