1. Note that Visit 3 is timed relative to Visit 1 but may be conducted on the same day as Visit 3a if Visit 3a occurs 24-28 days after Visit 1. Visit 3 and Visit 4 should not occur on the same day.
2. Note that Visit 4 is timed relative to Visit 2 and may be conducted on the same day as Visit 3a if Visit 3a occurs 24-28 days after Visit 2. Visit 3 and Visit 4 should not occur on the same day.
3. Symptom diary (solicited local and systemic reactogenicity events) to be completed by participant on Days 1-7 after vaccination.
4. Participants completing paper diary only will be called 2-4 days following Visits 1, 2, and 3 as a reminder and to prompt to bring paper diary to next visit
5. Electronic diary records will be reviewed by study staff at days 2-4 days and 8-10 days following Visit 1, 2 and 3.
6. If Visit 3a is conducted by telephone as standard of care these procedures do not need to be performed
7. HRQOL will only be collected for participants 12 years of age and older.
8. Receipt of BNT162b2 within 8 hours of enrollment is permitted
9. Receipt of BNT162b2 within 36 hours prior to study visit is permitted
10. Extended interval beyond 25 days not recommended for persons < 12 years of age

	Table 6: mRNA-1273 (Moderna) Schedule of Events										
Procedure	Visit 1	Visit 1a	Visit 2	Visit 2a	Visit 3 ¹	Visit 3a	Visit 3b	Visit 4 ²	Visit 5	Visit 6	Un-Scheduled
	Clinic	Phone/Text /Email/Data Review ^{3,4,5}	Clinic	Phone/Text /Email/Data Review ^{3,4,5}	Clinic	Phone/ Clinic	Phone/Text /Email/Data Review ^{3,4,5}	Clinic	Clinic	Phone	Clinic
Estimated Study Day (Relative to Visit 1)	1	1-7	8-15	8-15(+6)	29	29-57	29-57(+6)	36-43	57-85	121	
Time Following Visit 1 (Days) [Window]	0	0-6	7-14 [+2]		28 [+/-4]	28-56 [+/-4]				120 (+/-14)	
Time Following Visit 2 (Days) [Window]				0-6				28 [+/-4]			
Time Following Visit 3a (Days) [Window]							0-6		28 [+/-4]		
Informed consent & Medical Release of Information	X										
Review Eligibility Criteria	X										
Review Temporary Delay Criteria	X		X			X ⁶					
Demographic and Health History	X										
Influenza and COVID-19 Vaccination History	X										
Obtain unsolicited adverse events			X		X	X		X			
Obtain SAE and AESI information			X		X	X		X	X	X	X
Concomitant medications	X		X		X	X		X	X	X	X
Additional COVID-19 vaccinations										X	
HRQOL measure ⁷	X	X									
Measure temperature	X		X			X ⁶					X
Venipuncture	X				X ⁴			X ⁴	X		
Randomization	X										
Vaccination with COVID-19 vaccine	X ⁸					X ^{9,10}					

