### 3 STUDY ENDPOINTS

#### 3.1 Primary

- a) POM1a: Comparison of the proportion of participants reporting at least one solicited reactogenicity event to include fever, chills, myalgia, or arthralgia of moderate or greater severity in the Simultaneous group with the Sequential group within 1-7 days following Vaccination Visit 1 visit during which participants receive either IIV4 or placebo with an mRNA COVID-19 vaccine.

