## 8 ANALYSIS OF STUDY OBJECTIVES

### 8.1 Primary Objective

1. To compare the proportion of participants with moderate or more severe fever, chills, myalgia, or arthralgia in the group receiving IIV4 simultaneously with mRNA COVID-19 vaccine at Vaccination Visit 1 (Simultaneous group) with the group receiving IIV4 alone two weeks later at Vaccination Visit 2 (Sequential group) following both Vaccination Visit 1 and 2.
  - o *Research hypothesis: The proportion of participants with moderate or more severe fever, chills, myalgia or arthralgia will be noninferior (not higher) in the Simultaneous group versus the Sequential group.*

This objective will be assessed for visits 1 and 2 using a one-sided noninferiority test with the alpha level set at 0.025 and noninferiority margin of 10%. The null hypothesis is the Simultaneous group is inferior (i.e., Simultaneous group will have a higher proportion) to the Sequential group in regards to the proportion of participants with at least one moderate or severe fever, chills, myalgia, or arthralgia event after visits 1 and 2.

$$H_0: \text{Simultaneous group} - \text{Sequential group} \geq 0.10 \text{ (10\%)}$$

The alternative hypothesis is the Simultaneous group is noninferior to the Sequential group in regards to the proportion of participants with at least one moderate or severe fever, chills, myalgia, or arthralgia event after visits 1 and 2.

$$H_a: \text{Simultaneous group} - \text{Sequential group} < 0.10 \text{ (10\%)}$$

The upper bound of a site-stratified Newcombe binomial confidence interval (Yan and Su 2010) with Cochran-Mantel-Haenszel (CMH) weighting of the difference will be used to make these assessments with no adjustment to the alpha level for multiple comparisons.

See Tables 1 and 2 below for details.

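### The Visit 2 outcome window is not cut at COVID-19 dose 2, so in the BNT162b2 primary series some dose-2 reactions can be scored as reactions to IIV4 or placebo

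*SAP*

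**What the plan says.** **Endpoints.** SOM2a (SAP 3.2) covers events "within 1-7 days following Vaccination Visit 2 during which participants receive either IIV4 or placebo without an mRNA COVID-19 vaccine". The primary outcome in Protocol section 2 is measured "within 1-7 days following both Vaccination Visit 1 and Vaccination Visit 2", and SAP 8.1 agrees: "This objective will be assessed for visits 1 and 2 using a one-sided noninferiority test". SAP 3.1, however, defines the primary endpoint only "within 1-7 days following Vaccination Visit 1 visit during which participants receive either IIV4 or placebo with an mRNA COVID-19 vaccine". That conflict is separate and needs its own reconciliation.

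**Diary length.** Protocol 3.1: "Solicited reactogenicity events will also be monitored through Day 7 (total 7 days) following Visit 2 (all participants"), with the vaccination day as Day 1. Table 5 accordingly places the Visit 2 diary at 0 to 6 days after Visit 2.

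**Timing of dose 2.** In Protocol 5.1.1, Table 5 (BNT162b2), Visit 2 is at 7-14 days with a window of +2, and Visit 3a (dose 2) is at 21-56 days with a window of ±4. Both are counted from Visit 1, and no minimum gap between Visit 2 and Visit 3a is stated. The footnotes only keep Visits 3 and 4 off the same day. They add "Receipt of BNT162b2 within 36 hours prior to study visit is permitted" and "Extended interval beyond 25 days not recommended for persons < 12 years of age". The Background says that doses should not be given early, but that a dose "if given within a 4-day period prior to the scheduled time may be considered valid".

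**Attribution.** Under Protocol 5.4.1 all solicited symptoms are taken as vaccine-related and get no causality assessment. Protocol 5.4 records injection-site reactions separately by product; systemic symptoms have no such separation.

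**The concern.** SO2 is meant to compare IIV4 with saline when neither is given with a COVID-19 vaccine. If dose 2 falls within the Visit 2 diary, the days from dose 2 onward reflect a third injection that both arms receive. Protocol Table 1 shows that injection to be more reactogenic than dose 1 (BNT162b2, 16-55 years, any grade: chills 35.1% against 14.0%, muscle pain 37.3% against 21.3%).

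An example within the permitted windows: Visit 2 on day 14 after Visit 1, dose 2 on day 18, moderate chills on day 19. The Visit 2 diary covers days 14 to 20, so the chills count as a reaction to IIV4 or saline.

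The outcomes exposed are SO2, SOM3b, EOM2b, the unsolicited events of EOM3a, and the primary endpoint as defined in Protocol section 2 and SAP 8.1. Extra events that are equally likely in both arms pull an odds ratio toward 1. They also shrink a risk difference, which is the anti-conservative direction for a noninferiority test.

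**Working it through.** **1. The plan's power figure.** Inputs (Protocol 7.1.1, SAP 4.3): 15% in both groups, margin 0.10, 214 per group, one-sided alpha 0.025.

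Power = Φ(0.10/√(2 × 0.15 × 0.85/214) − 1.96) = Φ(2.897 − 1.960) = 82.56%, against the stated 82.6%. It reproduces.

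**2. Can the windows overlap?** Days are counted from Visit 1.
- Latest Visit 2: 14 + 2 = 16. Its diary ends at 16 + 6 = 22.
- Earliest BNT162b2 dose 2: 21 − 4 = 17.
- So up to six diary days (17 to 22) can follow dose 2.
- mRNA-1273: earliest dose 2 is 28 − 4 = 24, after day 22. No overlap.

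**3. How many permitted day pairs overlap?** A pair overlaps if dose-2 day ≤ Visit 2 day + 6.

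| Dose-2 day | Visit 2 days that overlap | Pairs |
|---|---|---|
| 17 | 11-16 | 6 |
| 18 | 12-16 | 5 |
| 19 | 13-16 | 4 |
| 20 | 14-16 | 3 |
| 21 | 15-16 | 2 |
| 22 | 16 | 1 |

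The total is 21, of which 18 need dose 2 before day 21. The other three need Visit 2 in its two grace days. In 6 of the 21 only one diary day is shared.

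| Permitted range (Visit 2 on days 7-16 unless stated) | Overlapping pairs |
|---|---|
| Dose 2 on days 17-60 | 21 of 10 × 44 = 440 |
| Dose 2 on days 17-25 (under-12 footnote) | 21 of 10 × 9 = 90 |
| Dose 2 on days 21-60 (never early) | 3 of 10 × 40 = 400 |
| Target days only (Visit 2 on 7-14, dose 2 on 21-56) | 0 of 288 |

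This uses the 0-6 day diary count. If the endpoint's 1-7 days is read instead as one to seven days after the visit, 28 of 440 pairs overlap, and the target ranges touch in one pair (Visit 2 on day 14, dose 2 on day 21). mRNA-1273 still gives none. The 36-hour allowance was not used.

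**4. Is there a rule that removes the overlap?** SAP 8.1 and 8.2 contain none. SAP section 9 covers only IIV4 and placebo given in the wrong order. SAP Appendix 1 applies only to the Immunogenicity Population.

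**5. Size, by illustration.** Let s be the share of all participants with overlap and q the chance of a qualifying event on the captured dose-2 days. The documents give neither, so both are assumed. With independent extra events, equal in both arms, each rate p becomes p + (1 − p)sq, and a risk difference is multiplied by (1 − sq). For SO2, Visit 2 rates of 8% (IIV4) and 3% (placebo) are also assumed, a true odds ratio of 2.81.

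| s | q | Sequential rate (15% planned) | Power | True 10-point difference becomes | Type I error at margin | SO2 odds ratio |
|---|---|---|---|---|---|---|
| 1% | 25% | 15.2% | 82.1% | 9.98 | 0.0254 | 2.68 |
| 2% | 25% | 15.4% | 81.7% | 9.95 | 0.0258 | 2.56 |
| 5% | 25% | 16.1% | 80.4% | 9.88 | 0.0269 | 2.29 |
| 10% | 25% | 17.1% | 78.4% | 9.75 | 0.0289 | 2.00 |

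First row: sq = 0.0025. The Sequential rate is 0.15 + 0.85 × 0.0025 = 0.1521. The SO2 rates are 0.08 + 0.92 × 0.0025 = 0.0823 and 0.03 + 0.97 × 0.0025 = 0.0324, an odds ratio of 2.68. This row would arise if 20% of the trial were in the BNT162b2 primary series and 5% of those overlapped.

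Across a wide assumed range (s 2-20%, q 15-40%), power runs from 82.0% to 70.7% and type I error from 0.0255 to 0.038. The upper end would need one participant in five in the whole trial to overlap.

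**The case against.** The strongest reply is that this is a rare edge case, and much of that stands.

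- The target schedule does not overlap on the diary count. Most overlapping pairs need an early dose 2, which the Background describes as something that should not be done but may be accepted as valid. Protocol 5.3.1 again gives approximately 21 to 56 days.
- Protocol 1.2 expects most adults and many children to be booster recipients, who have no study dose 2.
- Reactions in children aged 5-11 are described as generally mild to moderate. No moderate-or-worse rate is given for them, and the dose-2 percentages in Table 1 are any-grade in ages 16-55.
- Extra events also raise the variance and lower power, which works against declaring noninferiority. The primary effect is therefore not all in one direction.
- Under the Visit 1-only wording of SAP 3.1 the primary endpoint is untouched.

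Some stronger readings are tempting but unsupported:

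- A reader might infer that the overlap contradicts SOM2a. It does not: the phrase about no mRNA vaccine describes what is given at Visit 2 and does not limit the seven days.
- A reader might take 21 of 90 (23%) or 21 of 440 (5%) as the proportion of participants affected. They are equally weighted calendar pairs, and the documents give no distribution of visit dates.
- Nor can the 23% be applied to the whole primary series. It belongs to dose 2 on days 17-25, and mRNA-1273 recipients have no overlap. The under-12 footnote is a recommendation, not a limit.
- A reader might conclude that overlapping events are certainly counted twice, again in SOM3c and EOM1a. The definitions allow that, but the documents do not say how overlapping diary days are entered.

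None of this supplies the missing rule.

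**Conclusion.** The point holds as a gap in outcome attribution, limited to BNT162b2 primary-series participants with a late Visit 2, an early dose 2, or both. The permitted windows overlap by up to six days, and nothing in the analysis separates the systemic reactions.

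The bias is non-differential as long as dose-2 timing does not differ by arm, which the common schedule supports. SO2 is the more sensitive outcome because its event rates should be low: under the assumptions above, its odds ratio falls from 2.81 to 2.68 at 1% overlap and to 2.29 at 5%. The primary effect is small: at 1% overlap, type I error at the margin is 0.0254 and power 82.1%. The actual share affected is unknown and probably small. The documents do not support a claim that the primary conclusion is materially at risk. The change is still worth making, because it is cheap and avoids an ad hoc choice once the data are seen.

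**What to change.** In SAP 3.2 and 8.1 to 8.3, define the Visit 2 window as diary Days 1-7 after Visit 2, or up to the day before COVID-19 dose 2, whichever ends first. Assign diary entries from the dose-2 date onward to the third-vaccination outcomes only. Use the recorded dose-2 date rather than the Visit 3a date, since the dose may precede that visit. Apply the same cut to unsolicited events (EOM3a).

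The Visit 2a and Visit 3a windows in Table 5 should be reconciled with each other, and SAP 3.1 with SAP 8.1 and Protocol section 2.

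The cost is one SAP sentence and one line of derivation code. The planned sample size and the 82.6% power are unchanged. The downside is that a few primary-series participants will have a Visit 2 window shorter than seven days.

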#### 3.3 Exploratory

- a) EOM1a: Comparison of the proportion of participants reporting at least one solicited reactogenicity event to include fever, chills, myalgia, or arthralgia of moderate or greater severity in the Simultaneous group with the Sequential group within 1-7 days following Vaccination Visit 3 during which all participants receive an mRNA COVID-19 vaccine alone for those receiving two doses of mRNA COVID-19 vaccine.
- b) EOM2a. The proportion of participants reporting at least one moderate or greater or at least one severe or greater solicited local or systemic reactogenicity event in each

vaccination group within 1-7 days following the first vaccination during which participants receive either IIV4 or placebo with an mRNA COVID-19 vaccine.

EOM2b: The proportion of participants reporting at least one moderate or greater or at least one severe or greater solicited local or systemic reactogenicity event in each vaccination group within 1-7 days following the second vaccination visit which participants receive either IIV4 or placebo.

EOM2c: The proportion of participants reporting at least one moderate or greater or at least one severe or greater solicited local or systemic reactogenicity event in each vaccination group within 1-7 days following the third vaccination visit during which all participants receive an mRNA COVID-19 vaccine alone for those receiving two doses of mRNA COVID-19 vaccine.

EOM2d: The proportion of participants reporting at least one moderate or greater or at least one severe or greater solicited local or systemic reactogenicity event in each vaccination group within 1-7 days following all vaccination visits combined.

c) EOM3a: The proportion of participants in each vaccination group with an unsolicited adverse event occurring during the 7 days post each vaccination visit according to severity and system organ classification.

EOM3b: The proportion of participants in each vaccination group with an adverse event of special interest occurring during the study period according to event type.

d) EOM4a: Comparison between vaccination groups of the mean maximal change in score from baseline on the EuroQOL 5 dimensions-5 level (EQ-5D-5L) and EuroQOL visual analogue scale (EQ VAS) within 1-7 days following the first vaccination visit.

e) EOM5a: To compare secondary outcomes 3a, 3b, 3c and 4a according to baseline COVID-19 serostatus.

f) EOM6a: To compare secondary outcomes 3a, 3b, 3c and 4a according to COVID-19 vaccine product (Pfizer or Moderna).

g) EOM7a. The proportion of participants in each vaccination group with a seroprotective HAI titer ( $\geq 1:40$ ) pre- and post-IIV4 immunization for each IIV4 antigen.

EOM7b: The proportion of participants in each vaccination group achieving seroconversion following IIV4 (an HAI titer  $> 1:40$  following IIV4 if the baseline titer is  $< 1:10$  or a four-fold rise in HAI titer if the baseline titer is  $> 1:10$ ) for each IIV4 antigen.

EOM7c: The geometric mean HAI titer (GMT) for each IIV4 antigen pre- and post-IIV4 in each vaccination group.

EOM7d: The geometric mean fold rise (GMFR) in HAI titer for each vaccination group.

h) EOM8a: The proportion of participants in each vaccination group seropositive to SARS-CoV-2 variants tested prior to and following mRNA COVID-19 vaccine.

EOM8b: The geometric mean ID50 and ID80 titers of neutralizing antibodies for each SARS-CoV-2 variant tested pre- and post-mRNA COVID-19 vaccine in each vaccination group.

